**5.7.2.4 Supplementary Analysis**

No supplementary analyses will be performed.

**5.7.2.5 Subgroup Analysis**

No subgroup analyses will be performed.

**5.7.3 Analysis of Secondary Efficacy Endpoints****5.7.3.1 Endpoint, Treatment Effect and Estimand Definition**

Secondary efficacy endpoints and evaluations are summarised in following table:

**Table 1 Secondary Efficacy Endpoints and Evaluations**

Measure	Timepoint	Variable	Endpoint
Basal LH and FSH	Baseline, Month 3 and Month 6 (EOS)	LH and FSH concentration	Change in basal serum LH and FSH levels at Month 3 and Month 6 compared to baseline
Peak LH after GnRH	Baseline, Month 3 and	Peak LH levels after	Change in peak LH levels after GnRH stimulation test at

stimulation test	Month 6 (EOS)	GnRH stimulation (30, 60 and 90 minutes)	Month 3 and Month 6 compared to baseline; Proportion of children with LH suppression defined as stimulated peak LH $\leq 3$ IU/L after GnRH stimulation at Month 6.
Peak FSH levels after GnRH stimulation test	Baseline, Month 3 and Month 6 (EOS)	Peak FSH levels after GnRH stimulation (30, 60 and 90 minutes)	Change in peak FSH levels after GnRH stimulation test at Month 3 and Month 6 compared to baseline.
E2 and testosterone serum concentrations	Baseline, Month 3 and Month 6 (EOS)	Sex steroids levels	Proportion of children with sex steroids suppressed within prepubertal ranges (E2 $\leq 20$ pg/mL in girls and testosterone $\leq 0.3$ ng/mL in boys); Change in sex steroids levels compared to baseline
Pubertal stage (Tanner Method)	Baseline, Month 6 (EOS)	Pubertal stage	Change in pubertal stage (genital stage in boys, breast stage in girls and pubic hair stage in both sexes) compared to baseline; Proportion of children with stabilised pubertal stage compared to baseline
Auxological parameters (height, growth velocity, weight, BMI)	Baseline, Month 3 and Month 6 (EOS)	-	Change in auxological parameters compared to baseline
BA	Baseline, Month 6 (EOS)	-	Change in BA, difference between BA and CA compared to baseline
Uterine/ovary or testis volume	Baseline, Month 6 (EOS)	Gonad development	Change in uterine length in girls and testicular volume in boys compared to baseline

BA = Bone age; BMI = Body mass index; CA = Chronological age; E2 = Oestradiol; EOS = End of Study; FSH = Follicle-stimulating hormone; GnRH = Gonadotropin-releasing hormone; LH = Luteinising hormone.

### 5.7.3.2 *Secondary Analysis*

For secondary efficacy endpoints related to a change at Month 3, 6 compared to baseline, the descriptive summary statistics (number of participants (n), mean, SD, median, quartiles, minimum, maximum) will be calculated on the mITT.

Exact two-sided 90% CI will also be constructed for all secondary endpoints expressed as proportions.

GV cm/y, Height, Weight, BMI, FSH, LH values, Bone age, difference between Chronological age and Bone age, mean Oestradiol/Testosterone, Uterine Length and Testicular Volume over time will be graphically presented via individual observed values (scatter) as well as mean and standard deviation of the observed values (Baseline, Month 3, and Month 6).

### 5.7.3.3 *Sensitivity Analysis*

Secondary efficacy endpoints will be performed on the PPS using the same statistical method as mITT.

### 5.7.3.4 *Subgroup Analysis*

No subgroup analyses will be performed.

## 5.8 Safety (Main Phase)

### 5.8.1 *General Consideration*

All safety summaries and analyses will be based upon the Safety population. All safety data will be included in participant data listings (see listing detail conventions in Appendix A4). There will be no statistical comparison between the gender groups for safety data, unless otherwise specified within the relevant section.

If conversion factors are used, they should be presented either in the relevant section or a link to section 7 should be added.

All AEs will be recorded and graded according to the current version of the National Cancer Institute – Common Terminology Criteria for Adverse Events (NCI-CTCAE) Version 5.0.

### 5.8.2 *Extent of exposure*

Duration of exposure will be defined in days as:

Days of exposure = Date of Last Study Visit – First dose date + 1.

The following extent of exposure summaries will be presented:

- Summary of the duration of exposure to treatment, by gender. Provide the mean, median, and the count and percentage of participants exposed for specified periods of time choosing appropriate time intervals.
- Summary of the actual dose by gender. Provide the mean, median, sum and the count and percentage of participants exposed to specified dose levels choosing appropriate dose intervals.
- Summary of number of injections,
- Summary of total exposure,
- Listing of exposure data.

### 5.8.3 *Adverse Event*

All adverse events (AEs) recorded in the eCRF will be coded using the latest version of MedDRA dictionary in effect within IPSEN at the time of the database lock. AEs will be classified as treatment-emergent AEs (TEAEs) according to the rules below:

- Events with start date on or after the date of first IMP administration and up to the EOS or 185 days after first dose days which comes first.
- Events whose CTCAE grade worsens on or after the date of first IMP administration,
- Events whose causality changes to “Related” on or after the date of first IMP administration,
- Refer to appendix [Partial/Missing Date Convention A2](#) for handling of partial date. In the case where it is not possible to define an AE as treatment emergent or not, the AE will be classified by the worst case; i.e. treatment emergent.

Tabular summaries will be presented by gender. Summaries will include the number and percentage of participants and classified by primary system organ class and preferred term. The following summaries will be reported for AEs, TEAE regardless of drug relationship, TEAE related to study drug, TEAE grade 3 and above regardless of drug relationship, TEAE grade 3 and above related to study drug, serious AEs (SAEs), AE leading to study drug discontinuation, and AE leading to death:

- An overview table summarizing the number and percentage of participants with at least one of the following AEs: any AE; any TEAE; SAE, treatment emergent SAE, treatment-related TEAE, treatment emergent-related SAE, Non-serious TEAEs, TEAE leading to treatment discontinuation; TEAE leading to discontinuation from the study, CTCAE Grade  $\geq 3$  TEAE, Death, TEAE leading to death,
- A summary of the number and percentage of participants reporting a TEAE by gender, SOC and PT,
- A summary of the number and percentage of participants reporting a SAE by gender group and PT,
- A summary of the number and percentage of participants reporting a Serious TEAE by gender group and PT,
- A summary of the number and percentage of participants reporting a treatment-related Serious TEAE by gender group and PT,
- A summary of the number and percentage of participants reporting a TEAE leading to treatment discontinuation by gender group and PT,
- A summary of non-serious TEAE by gender group, SOC and PT,
- A summary of TEAE by gender group and PT,
- A summary of the number and percentage of participants reporting a TEAE by gender group, CTCAE grade, SOC and PT,
- A summary of the number and percentage of participants reporting a drug-related TEAE by gender group, CTCAE grade, SOC and PT,
- A summary of the number and percentage of participants reporting a TEAE by gender group, causality, SOC and PT,
- A summary of most frequent AEs (reported in  $> 5\%$ ) by gender group, SOC and PT.

AEs summaries will be ordered in term of decreasing frequency for SOC and PT within SOC in the gender, and then alphabetically for SOC and PT within SOC.

AEs will be counted as follows:

- Participants with more than one AE within a particular SOC are counted only once for that SOC. Similarly, participants with more than one AE within a particular PT are counted only once for that PT;
- Participants reporting a TEAE more than once within that SOC/ PT, the TEAE with the worst case CTCAE grade will be used in the corresponding CTCAE grade summaries;
- Participants reporting a TEAE more than once within that SOC/ PT, the TEAE with the worst case relationship to study medication will be used in the corresponding relationship summaries;
- If the CTCAE grade is missing for a TEAE, it will be considered as missing in the summary tables;
- If the causality is missing for a TEAE, it will be considered related in the summary tables;
- The non-serious TEAEs table should include a specific row “any non-serious TEAE above 10%;
- A TEAE is counted only in the study where it started (if there is a change in the CTCAE grade an additional AE should have been collected in the eCRF).

In addition, a listing with all AEs data will be listed by gender group including non-TEAEs, Treatment-emergence status will be flagged in the listing. Listing of Drug-related AEs will also be added.

The following listing will also be provided:

- A listing of all deaths that occurred during the study,
- A listing of all serious adverse events,
- A listing of all adverse events leading to discontinuation of study treatment.

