8.4 Local Tolerability

Assessment of local tolerability will be conducted as presented in the schedule of assessments (Table 1 and Table 2) and as described in this section.

After each triptorelin injection, the injection site will be examined, at injection and 2 hours post injection, by a physician or medical research associate and assessed for characteristics such as but not limited to tenderness, redness, bruising, erythema, swelling, rash, pain, itching, induration, haematoma, ulceration or necrosis. If present, the extent of erythema, haematoma, rash, ulceration or necrosis will be described and assessed quantitatively; this will at least include measurement of maximum length and maximum width.

Any reaction deemed clinically significant by the Investigator meets the definition of a TEAE, thus it needs to be reported in the eCRF as such, as indicated in Section 8.1.2.6.

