A TEAE is defined as any AE that occurs during the active phase of the study (between the start date of the treatment and the end of study treatment) if:

- It was not present prior to receiving the first dose of triptorelin, or
- It was present prior to receiving the first dose of triptorelin but the grade increased or became serious during the active phase of the study, or
- It was present prior to receiving the first dose of triptorelin, the grade/seriousness is the same but the causality changed to “related” during the active phase of the study.

All TEAEs will be flagged in the AE listings.

Summary incidence tables will be provided, classified by SOC, PT and associated NCI-CTCAE worst grade. In the event of multiple occurrences of the same AEs being reported for the same participant, the maximum intensity (Grade 5 > Grade 4 > Grade 3 > Grade 2 > Grade 1 > missing > not applicable) will be chosen. All AEs will be collected up to the EOS visit (see [Table 1](#) for schedule), or EOEP visit for those enrolled in the extension phase.

Concomitant medication will be coded by using World Health Organization Drug Dictionary (WHO-DD) version (current version in use at the start of the study) and will be summarised with the number and percentage of participants receiving concomitant medication by drug class and preferred drug name.

Haematological and biochemical toxicities will be recorded and graded according to the NCI-CTCAE criteria, where available. The NCI-CTCAE Grades 3 and 4 haematology and biochemistry variables will be listed by participant and by visit.

Actual values and changes from Baseline in clinical laboratory tests, physical examinations and vital signs will be summarised using descriptive statistics at each visit. For laboratory data, abnormal values will be flagged in the data listings and a list of clinically significant abnormal values will be presented. Shift tables using the worst on-treatment grade will be presented for the number and percentage of participants with NCI-CTCAE grades.

11.4.7 *Efficacy and Safety Evaluations (Extension Phase)*

A separate analysis on efficacy and safety endpoints will be performed considering the extension phase duration, a period of an additional 6 months, lasting until the End of Extension Phase Visit at Month 12.

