### ***Main study phase:***

A total of 32 participants, including three boys, will be enrolled in the study and treated with an intramuscular (i.m.) injection of triptorelin on Day 1 of the study and at Month 3 (3 months after the first injection). Triptorelin injections do not have to be adapted based on body weight but the participant should have a minimum weight of 20 kg.

[figure not shown]
The study consists of a Screening period (the Screening visit will take place up to 28 days before enrolment), during which participants with CPP will be screened for eligibility before receiving the first triptorelin injection (Day 1 of the study) and will visit the study centre at Month 3 and Month 6 for efficacy and safety assessments (Figure 1). Participants will receive a total of two injections during the study period before they attend the End of Study (EOS) visit at Month 6.

Each participant is expected to be enrolled in this study for a minimum of 6 months and up to 7 months (including Screening period).

Participants who complete the study will perform final procedures and assessments at the final visit (Month 6). Participants who withdraw from the study before the completion of the evaluation period will be invited to attend an Early Withdrawal visit to perform early discontinuation procedures and assessments.

The main study design is described in the following study flow chart.

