**2.6 Change from Statistical Section of the Protocol**

There is no change in SAP from statistical section of the protocol.

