### 5.1.4 *Reference Start Date and Study Day*

Reference start date is defined as the day of the first IMP administration.

The day of the first IMP administration will be Day 1. Study day will be calculated as:

- The difference between the event date and the reference date plus one day, if the event is on or after the reference date.
- The difference between the event date and the reference date, if the date of event is prior to the reference date.

Study day will appear in any listings where an assessment date or event date appears.

In case of partial or missing event date, study day will appear missing while any associated durations will be presented based on the imputations described in appendix [A2](#).

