### 5.9.2 Safety Endpoint for Extension Phase

The extension phase safety endpoints are the following;

- Incidence of treatment-emergent adverse events (TEAEs) throughout the study, including local tolerability
- Change in clinical safety laboratory (blood biochemistry, haematology and urinalysis) parameters at Months 9 and 12
- Change in physical examination and vital signs (blood pressure and heart rate) measurements at each visit

Unless otherwise specified, all the analysis of extension phase safety endpoints including AE, laboratory, physical examination and vital signs will be the same as main study phase.

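### The SAP's treatment-emergent window closes at about Month 6 and is carried unchanged into the extension, so extension TEAE tables would omit new events after that point

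*SAP*

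**What the plan says.** SAP 5.8.3 gives three routes by which an AE becomes treatment-emergent. A new event qualifies by its start date, on or after the first IMP administration and "up to the EOS or 185 days after first dose days which comes first". The other two routes, a worsening of CTCAE grade and a change of causality to related, have no end date.

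The anchor is fixed in SAP 5.1.4: "Reference start date is defined as the day of the first IMP administration". SAP 2.2 says that children receive two injections "before they attend the End of Study (EOS) visit at Month 6". The extension ends at a visit with a different name, EOEP, at Month 12.

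SAP 5.9.2 lists as an extension safety endpoint "Incidence of treatment-emergent adverse events (TEAEs) throughout the study, including local tolerability". It then says that, where the SAP gives no other rule, "all the analysis of extension phase safety endpoints including AE, laboratory, physical examination and vital signs will be the same as main study phase". SAP 5.9, the visit windows in SAP 6.1 and the TEAE date algorithm in Appendix A2 give no separate TEAE window for the extension.

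Protocol 11.4.6 defines a TEAE as "any AE that occurs during the active phase of the study (between the start date of the treatment and the end of study treatment"), with no 185-day limit, and collects AEs to EOEP for children in the extension. Protocol 8.4, which refers to the schedules of both phases, says of the injection-site check after each injection: "Any reaction deemed clinically significant by the Investigator meets the definition of a TEAE". SAP 2.6 states: "There is no change in SAP from statistical section of the protocol".

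**The concern.** The onset rule was written for a six-month study and is applied by reference to a twelve-month one. Extension children are injected at Month 6 and Month 9. The Month 6 injection is given at the EOS visit itself (Protocol 5.2.4), so only an event starting that same day falls inside the window. Every new event after the Month 9 injection falls outside it.

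At stake are the extension tables restricted to TEAEs: by SOC and PT, treatment-related, serious, grade 3 or higher, and leading to treatment discontinuation. They would hold almost no new events from the period they are meant to describe. Exposure in SAP 5.8.2 runs to the last study visit, so reported exposure would extend well beyond the period in which a new event can count.

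**Working it through.** **Inputs**

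- Protocol Table 1: first dose on Day 1; Month 6/EOS on Day 182 ± 3, so Day 179 to 185.
- Protocol Table 2: Month 9 injection on Day 271; EOEP on Day 365 ± 3, so Day 362 to 368.
- SAP 5.8.3: the window closes at the earlier of EOS and 185 days after first dose.

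**Where the 185 comes from.** 182 + 3 = 185, the top of the Month 6 visit window in study days. Because first dose is Day 1, 185 days after first dose is study Day 186. An EOS visit held within its window (Day 179 to 185) therefore always comes first and sets the limit.

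**Time outside the window** = EOEP day − closing day; share = that figure ÷ EOEP day.

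| Closing day | EOEP day | Days outside | Share of follow-up |
|---|---|---|---|
| 182 (nominal EOS) | 365 | 365 − 182 = 183 | 183/365 = 50.1% |
| 185 (latest EOS) | 365 | 365 − 185 = 180 | 180/365 = 49.3% |
| 179 (earliest EOS) | 365 | 365 − 179 = 186 | 186/365 = 51.0% |
| 185 | 362 | 362 − 185 = 177 | 177/362 = 48.9% |
| 179 | 368 | 368 − 179 = 189 | 189/368 = 51.4% |

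With both visit windows allowed to vary, the range is 177 to 189 days.

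**Within the extension.** Days 182 to 365 are 184 days. Only Day 182 is inside, so 183/184 = 99.5% is outside. Days 271 to 365, from the Month 9 injection onward, are 95 days, all outside.

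**More generous readings of the text**

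1. *Take EOS to mean the Month 12 visit for extension children.* The earlier limit still governs, and it is now study Day 186: 365 − 186 = 179 days outside, 179/365 = 49.0%. The Month 9 injection falls 271 − 186 = 85 days after the cap.
2. *Take first dose to mean the Month 6 injection.* SAP 5.8.3 and 5.1.4 tie the rule to the first IMP administration. EOS at Month 6 would still come first. Both limits would have to be rewritten.
3. *Rely on the SAP 5.8.3 counting rule that assigns a TEAE to the study in which it started.* That allocates events already classed as TEAEs. It does not class them.
4. *Rely on the worst-case default.* It applies only when TEAE status cannot be determined. A known start date of, say, Day 275 is determinably outside.
5. *Rely on grade worsening or causality change.* These routes stay open but do not cover new events.

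None of these readings brings new extension events into the window.

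**The case against.** The strongest reply is that the rule sits under the SAP's main-phase safety heading and suits that phase. Table 1 of the protocol collects main-study AEs up to the Month 6 visit, and the 185-day figure matches the top of that visit window. The intended extension analysis can be inferred: SAP 5.9 sets it over a further six months to Month 12, the endpoint covers the whole study, and TEAEs are to be counted where they start. A sensible programmer would probably not produce near-empty tables. That shows intent, and the problem looks like a drafting gap. It still supplies no window, and SAP 5.9.2 tells the programmer to use the main-phase method.

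The conflict with the protocol can also be called overstated. Protocol 11.4.6 is itself headed as main phase, does not date the end of study treatment, and gives no separate extension definition. That is true. But the same section collects AEs to EOEP for extension children, and even if the end of treatment means the last injection, that is Month 9 in the extension. Protocol 8.4 lies outside the statistical section, so it does not contradict SAP 2.6. It still conflicts with the SAP's rule for a clinically significant reaction after the Month 9 injection.

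Two limits stand in full. The percentages measure calendar time and do not estimate how far incidence is understated. They also apply only to children who choose the optional extension, at most 32.

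Finally, no data are lost. New extension events remain in the any-AE, SAE and death rows, the table of most frequent AEs, the local tolerability table and the listings. The analysis is descriptive and the primary endpoint is untouched. This limits the severity but does not repair the TEAE tables.

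**Conclusion.** The concern holds. As written, the onset rule excludes from the extension TEAE tables every event with a known start after about Month 6, unless it qualifies later through grade worsening or a causality change. That defeats a stated extension safety endpoint. On nominal visit days it removes 183 of 365 days of follow-up (177 to 189 days across the visit windows) and all but one day of the extension. The conclusion rests on applying SAP 5.8.3 literally through SAP 5.9.2, with visits held within their protocol windows; reading EOS as Month 12 does not change it. Laboratory, vital-sign and physical-examination summaries are unaffected. It should be fixed before the extension analysis is programmed, because the TEAE tables would otherwise disagree with the all-AE and SAE outputs beside them.

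**What to change.** In SAP 5.8.3 or 5.9.2, state that for children who enter the extension, TEAE onset runs from the first IMP administration to the EOEP or early withdrawal visit. Assign events with onset on or after the Month 6 injection to the extension and earlier ones to the main phase. Events starting on the day of that injection need a recorded time or a stated tie rule.

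Keep the existing limit (EOS or 185 days after first dose) only for children who do not enter the extension, and say whether it means study Day 185 or Day 186. Reconcile the wording with Protocol 11.4.6 and 8.4, and record any remaining difference from the protocol's statistical section in SAP 2.6.

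The cost is one SAP clause and one derivation on data already collected.

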(6) Is an important medical event that may not result in death, be life threatening, or require hospitalisation but, based upon appropriate medical judgement, may jeopardise the participant and may require medical or surgical intervention to prevent one of the outcomes listed in this definition. Examples of such medical events include allergic bronchospasm requiring intensive treatment in an emergency room or at home, blood dyscrasias or convulsions that do not result in in-patient hospitalisation, or the development of drug dependency or drug abuse.

Medical or scientific judgment should be exercised by the Investigator in deciding whether SAE reporting is appropriate in other situations such as significant medical events that may jeopardise the participant or may require medical or surgical intervention to prevent one of the other outcomes listed in the above definition. These events should usually be considered serious.

Examples of such events include invasive or malignant cancers, intensive treatment for allergic bronchospasm, blood dyscrasias, convulsions or development of intervention dependency or intervention abuse.

A suspected or confirmed coronavirus COVID-19 (SARS-CoV-2) infection must be reported as serious (seriousness criteria should be “other medically significant” if no other seriousness criteria are present (e.g. hospitalisation).

- **Hospitalisation** is defined as any in-patient admission (even if less than 24 hours). For chronic or long-term in-patients, in-patient admission also includes transfer within the hospital to an acute/intensive care in-patient unit
- **Prolongation of hospitalisation** is defined as any extension of an in-patient hospitalisation beyond the stay anticipated/required for the reason for the initial admission, as determined by the Investigator or treating physician. For protocol-specified hospitalisation in clinical studies, prolongation is defined as any extension beyond the length of stay described in the protocol. Prolongation in the absence

of a precipitating, TEAEs (i.e. not associated with the development of a new AE or worsening of a pre-existing condition) may meet the criteria for "seriousness" but is not an adverse experience and thus is not subject to immediate reporting to the Sponsor

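### SAP 5.8.3 omits the protocol's rule that a pre-dose event becoming serious after dosing is treatment-emergent, while SAP 2.6 declares no change from the protocol

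*SAP*

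**What the plan says.** Protocol 11.4.6 defines a TEAE as an event in the active phase that meets one of three criteria. The first is that the event was absent before the first dose. The second is: "It was present prior to receiving the first dose of triptorelin but the grade increased or became serious during the active phase of the study". The third applies where "the grade/seriousness is the same but the causality changed to" related. Because the third criterion holds both grade and seriousness fixed, the protocol treats them as two separate triggers.

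SAP 5.8.3 also has three rules:

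- "Events with start date on or after the date of first IMP administration", up to the end-of-study visit or 185 days after first dose, whichever comes first;
- "Events whose CTCAE grade worsens on or after the date of first IMP administration";
- "Events whose causality changes to" related, on or after first dose.

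SAP 2.6 states: "There is no change in SAP from statistical section of the protocol". Protocol section 11 allows the SAP to alter the plan, but the SAP declares no alteration here, and its history of changes does not mention the TEAE definition.

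**The concern.** The SAP is what the programmers will follow. If its TEAE rules are narrower than the protocol's, the treatment-emergent safety tables will apply a different definition from the one the protocol sets. A reader relying on SAP 2.6 would assume that the protocol's definition had been used. The omission works in one direction only: it can lower the treatment-emergent counts and cannot raise them.

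**Working it through.** The plan gives no figure on this point, so the check compares the two definitions rule by rule.

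| Event | Protocol 11.4.6 | SAP 5.8.3 |
|---|---|---|
| Onset after first dose | TEAE | TEAE (first rule) |
| Onset before first dose, grade rises | TEAE | TEAE (second rule) |
| Onset before first dose, causality changes to related | TEAE | TEAE (third rule) |
| Onset before first dose, becomes serious, same grade, causality not changed to related | TEAE | Not a TEAE |

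The definitions part only in the last row. The protocol's second criterion is met there, through "but the grade increased or became serious during the active phase of the study". All three SAP rules fail: onset is too early, the grade has not moved, and causality has not changed to related.

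**Does anything else in the SAP restore the criterion?**

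- The worst-case default in 5.8.3 applies only when treatment-emergent status cannot be determined. Here it can be.
- The note in 5.8.3 on an additional eCRF record covers a change in grade. It does not cover a change in seriousness.
- Appendix A2 deals only with partial and missing dates.

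**Is it version lag?** That is unlikely. SAP version 2.1 is dated 5 March 2022 and protocol version 4.0 is dated 9 July 2021. The Amendment 3 change table shows no edit to the TEAE definition.

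**Can the case arise?** AEs are collected from consent (Protocol 8.1), and screening can start up to 28 days before Day 1 (Protocol 5.1, Table 1), so pre-dose events can exist. Under Protocol 8.1.5 any in-patient admission counts as hospitalisation, including one shorter than 24 hours, and an important medical event is also serious. Either can make an event serious without raising its grade.

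**Which outputs change?** Missing: the treatment-emergent SAE row of the overview, the Serious TEAE table by preferred term, and the general TEAE tables. Unchanged: the all-SAE table, the listing of all SAEs, and the AE listing, which includes non-TEAEs and flags treatment-emergent status. The treatment-related Serious TEAE table is essentially unaffected, because an event that changes to related meets the third SAP rule.

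**Scale.** If all 32 planned children are in the Safety population, one such child is 1/32 = 3.1% of the denominator.

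**The case against.** The strongest reply is that the gap is narrow and its effect visible. Most of that stands.

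- A reader might infer that seriousness and grade are wholly independent, so that any event turning serious could be missed. The grade scale in Protocol 8.1.2.1 ties Grade 4 to life-threatening or disabling events and Grade 5 to death. Events that become serious by those routes will mostly rise in grade and meet the second SAP rule. What remains is admission or an important medical event at an unchanged grade.
- A reader might take COVID-19 as the natural example, since "A suspected or confirmed coronavirus COVID-19 (SARS-CoV-2) infection must be reported as serious". It is a poor one. An infection suspected during screening was already serious before dosing. If it is first diagnosed after dosing, Protocol 8.1.1 counts a newly diagnosed condition as an AE even if it may have been present earlier, and 8.1.5 asks for a diagnosis rather than symptoms. It would probably be a new record with post-dose onset, which the first SAP rule captures.
- A reader might infer that the SAE tables would disagree with no explanation. The overview has separate rows for SAEs and treatment-emergent SAEs, which are meant to be able to differ, and the AE listing flags which events are treatment-emergent.
- A reader might attach confidence limits to a count of one against zero. Main-phase AEs are planned as counts and percentages, so no planned main-phase AE output would shift in that way.
- Sites may enter a new record when seriousness changes, in which case the first rule captures the event. The eCRF instructions are not in the documents, and the SAP assumes a new record only for grade.

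None of this puts the missing criterion into the SAP or makes the statement in 2.6 accurate.

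**Conclusion.** The discrepancy holds and is minor. As written, SAP 5.8.3 omits one of the protocol's TEAE criteria and SAP 2.6 does not declare it. The textual finding is firm.

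The practical effect needs all of the following: onset between consent and first dose; the event still present at dosing; it becomes serious afterwards, in practice by admission or as an important medical event; the grade is unchanged; causality does not change to related; and the change is not entered as a new record with post-dose onset. Events meeting all of these are probably rare among about 32 children, and the documents give no rate from which to estimate how many. Where one occurs, the treatment-emergent tables understate by one participant, while the SAE is still reported elsewhere.

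**What to change.** Add a bullet to SAP 5.8.3 along these lines: *Pre-dose events that become serious from the first injection onward, within the active phase and up to the same end-of-window limit as new-onset events.* Stating the end of the window keeps the bullet in line with the protocol's active-phase restriction. SAP 5.9.2 already carries the main-phase AE analysis into the extension, so no separate bullet is needed there.

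Also have the date of a change in seriousness recorded, or have sites enter a new AE record when it changes, as the SAP already assumes for grade. Without one of these the derivation cannot tell whether an event became serious before or after dosing.

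If the narrower definition was intended, declare and justify it in SAP 2.6 instead.

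The cost is one SAP bullet, one line of derivation code and possibly one eCRF completion instruction.
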